2.1 Data analysis general information

Summary statistics for continuous variables include N, mean, standard deviation, minimum, lower quartile, median, upper quartile, and maximum. For binary or discrete variables the absolute number of subjects in each category and relative frequencies will be provided.

Unless otherwise specified, p-values will be presented as 2-sided p-values and the type I error rate (alpha) will be 5%.

Inferential efficacy comparison of secukinumab 300mg with adalimumab will be performed at Week 52 unless otherwise specified.

Efficacy and safety data for the entire treatment period will be presented by treatment groups.

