2.6.2 Statistical hypothesis, model, and method of analysis

The statistical hypothesis for monotherapy ACR20 is that there is no difference in the proportion of subjects fulfilling the monotherapy ACR20 criteria at Week 52 in the secukinumab 300 mg group vs. adalimumab.

Let p_j denote the proportion of monotherapy ACR20 responders at Week 52 for treatment regimens j , $j=0, 1$ where

0 corresponds to adalimumab,

1 corresponds to secukinumab 300 mg

In statistical terms, $H_0: p_1 = p_0$, $H_{1A}: p_1 \neq p_0$, i.e.

H_1 : secukinumab is not different to adalimumab regimen for signs and symptoms (monotherapy ACR20 response) at Week 52.

The primary endpoint of monotherapy ACR20 at Week 52 in the FAS will be evaluated using a logistic regression model with treatment as a factor and weight as a covariate. Odds ratios will

be computed for comparisons of secukinumab 300 mg vs. adalimumab regimen utilizing the logistic regression model fitted.

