- H₃: secukinumab 300 mg is not different to adalimumab regimen with respect to monotherapy ACR50 response at Week 52
- H₄: secukinumab 300 mg is not different to adalimumab regimen with respect to the change from baseline in HAQ-DI[®] at Week 52
- H₅: secukinumab 300 mg is not different to adalimumab regimen with respect to monotherapy resolution of enthesitis based on LEI at Week 52

The graphical approach of ([Bretz et al 2009](#)) for sequentially reject testing procedures is used to illustrate the testing strategy:

Figure 2-1 Hierarchical testing strategy

The family-wise error rate will be set to two-sided $\alpha=5\%$ and it will be controlled with the proposed hierarchical testing strategy. If H1 is rejected at α , each of the following hypotheses will be tested at α . If H2 is rejected at α , H3 will be tested at α and so on.

Monotherapy ACR50 at Week 52

Monotherapy response at Week 52 to ACR50 in the FAS will be evaluated using a logistic regression model with treatment as a factor and weight as a covariate.

Monotherapy PASI90 response

[figure not shown]
Monotherapy PASI90 response at Week 52 will be evaluated using a logistic regression model with treatment as a factor and weight as a covariate based on Psoriasis subset.

Physical function (HAQ-DI[®])

Between-treatment differences in the change in HAQ-DI[®] will be evaluated using a MMRM with treatment regimen, analysis visit as factors, and weight and baseline HAQ-DI[®] score as continuous covariates. Treatment by analysis visit and baseline by analysis visit will be included as interaction terms in the model. An unstructured covariance structure will be assumed for this model. The significance of the treatment effects for secukinumab regimen at different analysis visits will be determined from the pairwise comparisons performed between secukinumab regimen and adalimumab at the appropriate analysis visits.

Monotherapy Resolution of enthesitis

Monotherapy resolution of enthesitis based on LEI at Week 52 will be evaluated using a logistic regression model with treatment as a factor and weight as a covariate based on Enthesitis subset (LEI).

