****Buttocks are assessed as part of the Lower limbs (L) body region.

[figure not shown]
Because the head and neck, upper limbs, trunk and lower limbs correspond to approximately 10%, 20%, 30% and 40% of the body surface area, respectively, the PASI score is calculated using the formula:

[figure not shown]
$$\text{PASI} = 0.1(\text{E}_H + \text{I}_H + \text{D}_H)\text{A}_H + 0.2(\text{E}_U + \text{I}_U + \text{D}_U)\text{A}_U + 0.3(\text{E}_T + \text{I}_T + \text{D}_T)\text{A}_T + 0.4(\text{E}_L + \text{I}_L + \text{D}_L)\text{A}_L$$

[figure not shown]
The keys for the letters are provided in [Table 2-7](#).

[figure not shown]
PASI scores can range from a lower value of 0, corresponding to no signs of psoriasis, up to a theoretic maximum of 72.0. The total score comes from eCRF.

3 Sample size calculation

A family-wise error will be set to two-sided $\alpha=0.05$ to control for type I error. The primary objective of secukinumab 300 mg versus adalimumab with respect to ACR50/ACR20 response at Week 52 will be tested at a two-sided 0.05 alpha level.

An ACR20 response rate of about 50% for the TNF α inhibitor naïve without MTX use (monotherapy) population at week 48 was reported in Humira study ([Gladman 2007](#)). The response on secukinumab 300 mg is estimated to be 62% in the TNF α inhibitor naïve monotherapy population based on the lower bound of 80% confidence interval of Meta-analysis results of the study FUTURE2 ([McInnes 2015](#)) and unpublished study FUTURE3. With 425 subjects per treatment group there would be approximately 94% power to detect a treatment difference of 12% at a two-sided 0.05 alpha level in ACR20 response rates (Chi Square test, NQuery 7.0) between secukinumab 300 mg and adalimumab in the evaluation of the primary efficacy hypothesis at Week 52. The overall sample size will be 850 patient for a randomization ratio of 1:1 (secukinumab 300mg 425 patients, and adalimumab 425 patient). The estimated power with the chosen sample size for other efficacy endpoints based on the data available for adalimumab and meta-analysis results of the study FUTURE2 and study FUTURE3 are summarized in [Table 3-2](#).

Table 3-1 Assumption for sample size and power calculation

Endpoint	Secukinumab 300 mg expected values	Adalimumab (N=76) observed values
ACR20	62%	50%
PASI90	63%	38% (N=40)
ACR50	49%	38%
HAQ-DI change*	-0.59 (0.5)	-0.4 (0.5)(N=61)
Resolution of enthesitis	61%	33%

*mean (standard deviation)

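### The PASI90 (H2) and enthesitis (H5) models adjust for weight alone; prespecifying the baseline LEI site count, and with less expected gain baseline PASI, would be a cheap but optional efficiency gain

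*SAP*

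**What the plan says.** SAP 2.7 tests PASI90 (H2) by logistic regression on treatment, with "weight as a covariate based on Psoriasis subset". Resolution of enthesitis (H5) is tested the same way, "with treatment as a factor and weight as a covariate based on Enthesitis subset (LEI". The primary endpoint in SAP 2.6.2 uses the same form, a "logistic regression model with treatment as a factor and weight as a covariate", and so does ACR50. The code in SAP 6.2.2.2, and the GENMOD step run on the imputed data in 6.2.2.4, contain treatment and weight only.

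HAQ-DI (H4) is handled differently. Its MMRM has the baseline score as a covariate, and "Treatment by analysis visit and baseline by analysis visit will be included as interaction terms in the model".

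The unused baseline measures exist. SAP 2.12.3.1 names six LEI sites and calls enthesitis present if any one is involved. SAP 2.2 uses that presence at baseline to define the enthesitis subset. Baseline values, including PASI, enter the imputation model in 6.2.2.4. SAP 2.6.3 excludes patients with missing baseline values from the subset analyses.

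SAP section 3 (Tables 3-1 and 3-2) plans on 63% v 38% for PASI90 and 61% v 33% for enthesitis, with 213 per arm in each subset, and states 99% power for both.

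**The concern.** Resolution of enthesitis means that none of the six sites is involved. A patient who starts with one involved site and a patient who starts with six face very different hurdles, so the baseline count is a natural prognostic factor. The plan reduces it to presence or absence, which is the same for everyone in the subset. Baseline PASI is a weaker candidate.

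Protocol 5.3 describes no stratification factors, so nothing in the design balances baseline severity within these two subsets. H2 gates H3 to H5, and H5 is planned on about half of the patients. If the true effects were well short of plan, a few points of power could matter, and the information needed to gain them is already in the database.

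**Working it through.** **1. The plan's own power.** Inputs from SAP section 3: 1:1 allocation, 213 per arm, two-sided 5%. Formula: power = Φ[(p1 − p0 − 1.96·SE0)/SE1], where SE0 = √(2·p̄·(1−p̄)/n) and SE1 = √((p1(1−p1) + p0(1−p0))/n).

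- H2, 63% v 38%: p̄ = 0.505, SE0 = 0.04845, SE1 = 0.04691. Then (0.25 − 0.09496)/0.04691 = 3.305, and power is 99.95%.
- H5, 61% v 33%: p̄ = 0.47, SE0 = 0.04836, SE1 = 0.04642. Then (0.28 − 0.09479)/0.04642 = 3.990, and power is 99.997%.

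Both agree with the stated 99%. By the same method, 90% power needs only 82 (H2) and 65 (H5) per arm.

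**2. The testing sequence.** If the tests were independent, the chance of rejecting H1 to H5 is 0.9424 × 0.9995 × 0.9002 × 0.9998 × 0.99997 = 84.8%. Setting H2 and H5 to 1 leaves it at 84.8%. H1 and H3 are the limits.

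**3. What adjustment does at the planned rates.** Simulation: 2,000 trials per setting, a normally distributed baseline covariate, no weight effect, no missing data. The documents give no prognostic strength, so an odds ratio (OR) of 1 to 3 per SD is assumed. With 213 per arm, H2 power is 99.85–100% with weight alone and 99.9–100% with the covariate added; H5 is 100% either way. The SE of the H2 log odds ratio rises from 0.201 to 0.207, 0.215 and 0.231 at OR 1.5, 2 and 3 per SD. The estimate moves away from zero by more than this, so power does not fall.

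**4. Smaller effects, H5.** Take 61% v 50%. The formula in step 1 gives p̄ = 0.555, SE0 = 0.04816, SE1 = 0.04786 and (0.11 − 0.09439)/0.04786 = 0.326, so unadjusted power is 63%. A simulation of 4,000 trials, with an assumed distribution of 1 to 6 sites, gave:

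| Assumed OR per extra site | Power, weight only | Power, plus LEI count | Gain in z² |
|---|---|---|---|
| 0.8 | 63% | 65% | 2.5% |
| 0.7 | 62% | 65% | 6% |
| 0.6 | 62% | 68% | 12% |

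As a cross-check, to first order the gain is p̄(1−p̄)·β²·σ², where β is the log OR per site and σ the SD of the count. Here p̄(1−p̄) = 0.247 and β² = 0.0498, 0.127 and 0.261, so the three gains imply σ² = 2.0, 1.9 and 1.9, that is, an SD of about 1.4 sites throughout. A narrower spread of counts would shrink the gain in proportion to σ².

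Over the same range of assumptions the variance of the standardised risk difference falls by about 2% to 12%, while the SE of the conditional log odds ratio rises from 0.197 to 0.200–0.210.

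**5. Effects halved, 213 per arm** (simulation of step 3; Monte Carlo error about 1 point). With OR 1.5, 2 and 3 per SD:

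- H2, 50.5% v 38%: power goes from about 75% to 77%, 79% and 83%.
- H5, 47% v 33%: power goes from about 84% to 84%, 88% and 91%.

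**The case against.** The strongest reply is that nothing is lost at the plan's own inputs: step 3 shows a change of 0.2 points or less, and step 2 shows that the sequence is limited elsewhere. That stands. It is also fair that every prognostic strength above is assumed, and that the top of the range is steep. An OR of 0.6 per site means 0.6^5 = 0.078, about 13-fold lower odds of resolution with six sites than with one.

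The reply is not complete, because the planned rates are uncertain. The 38% for adalimumab PASI90 rests on 40 patients; a Wilson 95% interval for 15/40 is 24% to 53%. Against 63% with 213 per arm, power is 96%, 77% and 55% at control rates of 45%, 50% and 53%. Tables 3-1 and 3-2 also do not mention the monotherapy composite that is now analysed.

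A reader might infer more than the documents support:

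- **That precision of the reported odds ratio is being lost.** In logistic regression a prognostic covariate raises the SE of the log odds ratio and changes which conditional odds ratio is estimated. The gain is in power and in the risk difference.
- **That chance imbalance makes the tests invalid.** Under randomisation the type I error of the prespecified weight-only test already allows for it.
- **That the HAQ-DI model shows an inconsistency.** HAQ-DI is a continuous change score in an MMRM. The confirmatory binary endpoints all share one model, so the plan is consistent by endpoint type.
- **That the protocol already covers the point.** Protocol 9.4.4 permits further logistic models with other baseline characteristics, but only optionally and as support for the primary endpoint.

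**Conclusion.** The observation holds: H2 and H5 adjust for weight only, while a baseline severity measure for each is collected. It is an optional efficiency improvement of low priority. The planned tests are valid and have more than 99.9% power at the planned rates.

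For H5 the gain is about 2 to 6 power points at 61% v 50%, with a 2% to 12% smaller variance of the standardised risk difference. This assumes 213 per arm, odds ratios of 0.8 to 0.6 per site and a reasonable spread of baseline counts. For H2 the gain is less certain, because PASI90 is already a relative change from baseline PASI and the documents do not show how far baseline PASI predicts it. The case for the LEI count is therefore the stronger of the two. No gain was calculated for ACR20 or ACR50, so the point does not extend to them.

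**What to change.** Before unblinding:

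- **H5:** use `model aval = trt_ weight base_LEI_count` in SAP 2.7, 6.2.2.2 and the GENMOD step of 6.2.2.4.
- **H5 imputation:** add the baseline LEI count to the enthesitis imputation model in 6.2.2.4. It now has Baseline as a class variable; if that is presence or absence, it is constant in this subset. Without this step the analysis model would be richer than the imputation model.
- **H2:** with less expected gain, use `model aval = trt_ weight base_PASI` in the same three places. Baseline PASI is already in its imputation model.
- **Reporting:** give a standardised risk difference beside each odds ratio.

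A lighter alternative is to prespecify these models as sensitivity analyses. The cost is a small amount of code and an odds ratio that is conditional on one more covariate. Few or no patients should be lost, since SAP 2.6.3 already excludes those with missing baseline values from the subset analyses. Added after unblinding, the same models would be post hoc.

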2.9 Safety analyses

Safety analyses will be performed on treatment received or actual treatment as described below:

The actual treatment or treatment received for summaries of safety data will differ to the treatment assigned at randomization only if a subject received the wrong treatment during the entire study.

For those subjects who received not the treatment randomized, i.e. who received erroneously the wrong treatment at least once, an additional AE listing will be prepared displaying which events occurred after the treatment errors.

2.9.1 Adverse events (AEs)

The crude incidence of treatment emergent adverse events (TEAEs) (i.e. events started after the first dose of study treatment or events present prior to the first dose of study treatment but increased in severity based on preferred term and on or before last dose + 84 days) will be summarized by primary system organ class and preferred term. Confidence intervals for the crude rate will be derived as described in [Section 5.2.4.1](#). Graphical displays of the crude incidence rates will be presented for all AEs and serious AEs by system organ class.

Adverse events reported will be presented first by alphabetical order of system organ class and then in descending frequency according to its incidence in secukinumab group starting from the most common event. For ties in incidence rate of secukinumab group, sort adverse events by incidence rate of adalimumab group. Summaries (crude incidences only) will also be presented for AEs by severity and for study treatment related AEs. If a particular AE 'severity' is missing, this variable will be listed as missing and treated as missing in summaries. If a subject reported more than one adverse event with the same preferred term, the adverse event with the greatest severity will be presented. If a subject reported more than one adverse event within the same primary system organ class, the subject will be counted only once with the greatest severity at the system organ class level, where applicable.

Separate summaries will be provided for adverse events suspected to be related to study drug, deaths, serious adverse events, and adverse events leading to discontinuation and adverse events leading to temporary dose interruption.

Adverse events will also be reported separately by SMQ according to MedDRA. The MedDRA version used for reporting the study will be described in a footnote.

Non-treatment emergent adverse events will be listed.

Algorithms for date imputations will be provided in RAP Programming Dataset Specification (PDS).

For serious adverse events (SAEs) occurred during screening a listing will be prepared for all subjects screened including screening failures.

When adjudication is required of major cardiovascular events, a listing of those types of events as reported by the investigator and confirmed by adjudication will be provided.

The safety analyses that will be performed for treatment emergent AEs and on treatment labs, ECG and vital signs for the analysis period is described in [Table 2-1](#).

Table 2-1 Overview of analyses on some safety endpoints

Analysis period	AEs & SAEs	AEs by severity	Study-drug related AEs	Risk	Notables for (vitals/ECG), lab criteria
Entire treatment	Cruide incidence	Cruide incidence	Cruide incidence	Cruide incidence	Cruide incidence

2.9.2 Laboratory data

The summary of lab data will only include on treatment data, which are defined as those lab assessments after the first dose of study treatment and on or before last dose + 84 days.

The summary of laboratory evaluations will be presented for three groups of laboratory tests (hematology, chemistry and urinalysis). In addition to the individual laboratory parameters the ratios “total cholesterol / HDL” will be derived and summarized.

For urinalysis, frequency tables will be presented.

Descriptive summary statistics for the change from baseline to each study visit will be presented. These descriptive summaries will be presented by laboratory test and treatment group. Change from baseline will only be summarized for subjects with both baseline and post baseline values and will be calculated as:

$$\text{change from baseline} = \text{post baseline value} - \text{baseline value}$$

For each parameter, the maximum change (maximum decrease and maximum increase) from baseline, if appropriate for each study phase, will be analyzed analogously.

In addition, shift tables will be provided for all parameters to compare a subject’s baseline laboratory evaluation relative to the visit’s observed value. For the shift tables, the normal laboratory ranges will be used to evaluate whether a particular laboratory test value was normal, low, or high for each visit value relative to whether or not the baseline value was normal, low, or high. If appropriate, the shifts to the most extreme laboratory test value within a treatment phase (either initial or entire) will be presented as well (including category “high and low”). These summaries will be presented by laboratory test and treatment group.

The following laboratory parameters will be analyzed with respect to numerical Common Terminology Criteria for Adverse Events (CTCAE) grades, given in [Table 2-2](#): hemoglobin, platelets, white blood cell count, neutrophils, lymphocytes, creatinine, total bilirubin (TBL), gamma-glutamyl transferase (GGT), alanine aminotransferase (ALT), aspartate aminotransferase (AST), alkaline phosphatase (ALP), glucose, cholesterol, triglycerides (TG).

These summaries will be split into hematology and chemistry for study level reports and the pooled summary of clinical safety (SCS).

Table 2-2 CTCAE grades for laboratory parameters to be analyzed

CTCAE v4.0 Term	Grade 1	Grade 2	Grade 3	Grade 4
HGB decreased (Anemia)	<LLN – 100 g/L	<100 – 80 g/L	<80 g/L	
Platelet count decreased	<LLN – 75.0 x10e9 /L	<75.0 - 50.0 x10e9 /L	<50.0 – 25.0 x10e9 /L	<25.0 x 10e9 /L
White blood cell decreased	<LLN - 3.0 x 10e9 /L	<3.0 - 2.0 x 10e9 /L	<2.0 - 1.0 x 10e9 /L	<1.0 x 10e9 /L

CTCAE v4.0 Term	Grade 1	Grade 2	Grade 3	Grade 4
Neutrophil count decreased	<LLN - 1.5 x 10e9 /L	<1.5 - 1.0 x 10e9 /L	<1.0 - 0.5 x 10e9 /L	<0.5 x 10e9 /L
Lymphocyte count decreased	<LLN - 0.8 x 10e9/L	<0.8 - 0.5 x 10e9 /L	<0.5 - 0.2 x 10e9 /L	<0.2 x 10e9 /L
Creatinine increased*	>1 - 1.5 x baseline; >ULN - 1.5 x ULN	>1.5 - 3.0 x baseline; >1.5 - 3.0 x ULN	>3.0 baseline; >3.0 - 6.0 x ULN	>6.0 x ULN
TBL increased	>ULN - 1.5 x ULN	>1.5 - 3.0 x ULN	>3.0 - 10.0 x ULN	>10.0 x ULN
GGT increased	>ULN - 2.5 x ULN	>2.5 - 5.0 x ULN	>5.0 - 20.0 x ULN	>20.0 x ULN
ALT increased	>ULN - 3.0 x ULN	>3.0 - 5.0 x ULN	>5.0 - 20.0 x ULN	>20.0 x ULN
AST increased	>ULN - 3.0 x ULN	>3.0 - 5.0 x ULN	>5.0 - 20.0 x ULN	>20.0 x ULN
ALP increased	>ULN - 2.5 x ULN	>2.5 - 5.0 x ULN	>5.0 - 20.0 x ULN	>20.0 x ULN
Glucose increased (Hyperglycemia)	>ULN - 8.9 mmol/L	>8.9 - 13.9 mmol/L	>13.9 - 27.8 mmol/L	>27.8 mmol/L
Glucose decreased (Hypoglycemia)	<LLN - 3.0 mmol/L	<3.0 - 2.2 mmol/L	<2.2 - 1.7 mmol/L	<1.7 mmol/L
Cholesterol high	>ULN - 7.75 mmol/L	>7.75 - 10.34 mmol/L	>10.34 - 12.92 mmol/L	>12.92 mmol/L
Hypertriglyceridemia	1.71 - 3.42 mmol/L	>3.42 - 5.7mmol/L	>5.7 - 11.4 mmol/L	>11.4 mmol/L

*Note: for "creatinine increased" the baseline criteria do not apply

Shift tables will be presented comparing baseline laboratory result (CTCAE grade) with the worst results (expressed in CTCAE grade) during the treatment phase (either initial or entire) analyzed. Of note, baseline will be defined as last assessment prior to first dosing in initial treatment phase. Subjects with abnormal laboratory values will be listed and values outside the normal ranges will be flagged.

Summaries for newly occurring or worsening clinically notable lipid abnormalities will also be provided cumulatively for each of the following parameters and categories:

- HDL:
 - \leq LLN
 - $<0.8 \times$ LLN
- LDL, cholesterol, triglycerides:
 - \geq ULN
 - $>1.5 \times$ ULN
 - $>2.5 \times$ ULN

Newly occurring or worsening liver enzyme abnormalities will also be summarized based on the event criteria given in [Table 2-3](#):

Table 2-3 Liver-related events

Parameter	Criterion
ALT	>3xULN; >5xULN; >8xULN; >10xULN, >20xULN
AST	>3xULN; >5xULN; >8xULN >10xULN; >20xULN
ALT or AST	>3xULN; >5xULN; >8xULN >10xULN; >20xULN
TBL	>1.5xULN, >2xULN, >3xULN,
ALP	>2xULN, >3xULN. >5xULN
ALT or AST & TBL	ALT or AST >3xULN & TBL >2xULN; ALT or AST >5xULN & TBL >2xULN; ALT or AST >8xULN & TBL >2xULN; ALT or AST >10xULN & TBL >2xULN
ALP & TBL	ALP >3xULN & TBL >2xULN ALP >5xULN & TBL >2xULN
ALT or AST & TBL & ALP	ALT or AST >3xULN & TBL >2xULN & ALP <2xULN (Hy's Law) Note: elevated ALP may suggest obstruction as a consequence of gall bladder or bile duct disease; ALP may also be increased in malignancy. FDA therefore terms Hy's Law cases as indicators of pure hepatocellular injury . This does not mean that cases of ALT or AST >3xULN & TBL >2xULN & ALP ≥2xULN may not result in severe DILI.

Notes:

1) In studies which enroll subjects with pre-existing liver disease, baseline LFT may be increased above ULN; in such a case it is meaningful to add the condition "and worse than baseline" to the abnormality criteria

For a combined criterion to be fulfilled, all conditions have to be fulfilled on the same visit. The criteria are not mutually exclusive, e.g. a subject with ALT = 6.42xULN is counted for ALT >3xULN and ALT >5x ULN.

Individual subject data listings will be provided for subjects with abnormal laboratory data. Data of subjects with newly occurring or worsening liver enzyme abnormalities will be listed in an additional listing.

Box plots over time will be presented for selected laboratory parameters (neutrophils, liver and lipid parameters).

In addition, three individual subject data listings will be provided for liver events, laboratory values and viral serology, autoimmunity, imaging, pathology, drug abuse for patients with liver events.

The laboratory values below Lower Level of Quantification (LLQ) or above Upper Level of Quantification (ULQ) will be imputed as LLQ or ULQ, respectively. The numerical part of the reported result will be treated as the actual LLQ or ULQ. These laboratory values will be displayed in listings using the standard unit with the reported sign (" $<$ " or " $>$ ")."

